8.4.2.2 Safety Outcome Measures (Parts 1 and 2)

1. The incidence and severity of all AEs, related AEs, all SAEs, related SAEs and temporally-associated AEs
2. Change from baseline in clinical laboratory safety parameters and vital signs
3. Incidence of recurrence of primary malignancies through Days 180 and 365
4. Incidence and type of infection (eg, bacterial, fungal, viral, etc) at Days 28, 56, 180 and 365

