10.6 Subject Completion/Discontinuation

A subject is considered to have completed the study when he/she ceases active participation in the study according with the protocol (with or without protocol deviations).

Reasons for completion/discontinuation will be reported on the Completion/Discontinuation CRF, including: completed, screen failure, AE (eg, death), discontinuation by subject (eg, lost to follow-up [defined as 3 documented unsuccessful attempts to contact the subject], dropout), physician decision (eg, pregnancy, progressive disease, non-compliance with IP/protocol violation(s), recovery), study terminated by sponsor, or other (reason to be specified by the investigator, eg, technical problems). Regardless of the reason, all data available for the subject up to the time of completion/discontinuation through the study follow-up period should be recorded on the appropriate CRF.

Every effort will be made to have discontinued subjects complete the study completion/termination visit. If the study completion/termination visit is done as an additional, unscheduled visit, the assessment results shall be recorded with the study completion/termination visit. If a subject terminates participation in the study and does not return for the study completion/termination visit, their last recorded assessments shall remain recorded with their last visit. The reason for discontinuation will be recorded, and the data collected up to the time of discontinuation will be used in the analysis and included in the clinical study report. If additional assessments are required, the assessments shall be recorded separately. Assessments to be performed at the study completion/termination visit (including in cases of withdraw or discontinuation) can be found in Supplement 20.2 Schedule of Study Procedures and Assessments.

Subjects who discontinue study treatment prior to Day 28 will complete the Day 28 visit on Day 28 (± 1 day). If at least 2 weeks have passed since the last dose of study treatment, the Day 28 visit will serve as the study completion/termination visit. If Day 28 is less than 2 weeks following the last dose of study treatment, subjects will complete the Day 28 visit and then the study completion/termination visit 2 weeks (± 1 day) after the last dose of study treatment. In this event, the study completion/termination visit will consist of an office visit with the same assessments as the Day 365 visit.

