Subjects who discontinue study treatment after Day 28 will complete the study completion/termination visit as an office visit 2 weeks (± 1 day) after the last dose of study treatment. Subjects who withdraw from the study after Day 56 will be encouraged to complete the study completion/termination visit at the time of discontinuation. In the event that it is not feasible for the subject to visit the site at the study completion/termination visit after Day 56, the visit may be conducted with a phone call.

Subjects who discontinue study treatment will not attend any other subsequent visits other than Day 28 and the study completion/termination visit (if applicable), except as needed for follow-up of recovering/resolving AEs (see Section 12.1.2).

In the event of subject discontinuation due to an AE, clinical and/or laboratory investigations that are beyond the scope of the required study observations/assessments may be performed as part of the evaluation of the event. These investigations will take place under the direction of the investigator in consultation with the sponsor, and the details of the outcome may be reported to the appropriate regulatory authorities by the sponsor.

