12.1.2 Assessment of Adverse Events

For the purposes of this study, changes in the severity or duration of GvHD experienced after the first IP exposure are collected as an efficacy endpoint and thus are not reportable on the AE CRF, nor will they be included in the analysis of AEs.

Symptoms or diagnostic findings of GvHD, such as skin rashes, abnormal liver function tests, diarrhea, ileus and bowel perforation, should be collected on the AE CRF only if there is an increase in the severity, duration or frequency AND if they begin after first exposure to IP.

All other AEs from the first IP exposure until study completion will be described on the AE CRF using the medical diagnosis (preferred), or, if no diagnosis could be established at the time of reporting the AE, a symptom or sign, in standard medical terminology in order to avoid the use of vague, ambiguous, or colloquial expressions (see definition in Section 12.1). Each AE will be evaluated by the investigator for:

- Seriousness as defined in Section 12.1.1.1
- Severity as defined in Section 12.1.2.1
- Causal relationship to IP exposure or study procedure as defined in Section 12.1.2.2

For each AE, the outcome (ie, recovering/resolving, recovered/resolved, recovered/resolved with sequelae, not recovered/not resolved, fatal, unknown) and if applicable action taken (ie, dose increased, dose not changed, dose reduced, drug interrupted, drug withdrawn, not applicable or unknown) will also be recorded on the AE CRF. Recovering/resolving AEs will be followed until resolution or 30 days after the study completion/termination visit, whichever comes first. The follow-up information will be documented in the AE CRF. If the severity rating for an ongoing AE changes before the event resolves, the original AE report will be revised (ie, the event will not be reported as separate AE). During the course of any AE, the highest severity rating will be reported.

Deviations from protocol-specified procedures of IMP use such as overdosing, underdosing, withdrawal, omission, incorrect route of administration, and use of a product other than the IMP, standard care of the underlying disease or treatment of a TEAE shall be recorded in the Protocol Deviation Form.

Any pregnancy that occurs after administration of IP will be reported on a Pregnancy Report Form.

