13. STATISTICS

13.1 Sample Size and Power Calculations

Part 1:

The sample size for Part 1 was determined from an operational perspective and was not based on statistical power considerations. With 20 evaluable subjects and an assumed true response rate of 65%, the probability of observing an overall response rate of at least 55% is 87.8%. If the true response rate is 40%, the probability of observing an overall response rate of 55% or higher is less than 13%.

Part 2:

The primary endpoint for Part 2 is the overall response rate at Day 28.

The null hypothesis for Part 2 is that there is no difference in the overall response rate at Day 28 between the 2 treatment groups. The alternative hypothesis is that the overall response rate at Day 28 of the GLASSIA group is higher than that of the control group.

To determine the sample size for Part 2, the following assumptions were used:

1. Control group overall response rate of 40% across strata
2. GLASSIA group overall response rate of 65% across strata
3. Randomization ratio 1:1
4. 1-sided family wise Type I error rate of 0.025
5. Type II error rate of 0.20 (ie, power=80%)
6. A group sequential design with 1 interim look will be applied to the study. The gamma error spending function³¹ with a parameter -2 will be used for beta spending (nonbinding). The interim analysis will take place when approximately 50% of the primary endpoint data has been accumulated

SAS version 9.4, PROC SEQDESIGN with stop=both and nonbinding option for beta, and a gamma parameter of -40 for alpha spending (and hence no alpha spent) and -2 for beta spending was used to calculate this design.

Based on the sample size calculations, using a Cochran-Mantel-Haenszel chi-squared test, controlling the stratification factor, to detect the difference between the 2 groups, the primary analysis will require 67 evaluable subjects per group. Assuming a 10% early withdrawal rate, the target number of subjects will include 74 randomized subjects per group for a total of 148 randomized subjects.

The early withdrawal rate will be monitored in a blinded manner, and if found to be greater or less than 10%, sample size assumptions may be revised.

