13.4.2 Secondary Outcome Measures

Part 1

The secondary efficacy outcome measures (see Section 8.4.2.1) and the secondary PK outcome measures (see Section 8.4.2.3) will be summarized with descriptive statistics. PK parameters will be summarized with the mean, SD, median, minimum and maximum values, geometric mean and percentage of coefficient of variation.

Part 2

The key secondary endpoint of GI response rate at Day 28 (see Section 8.4.2.1) and all binary types of endpoints, including overall response at Day 56, will be analyzed similarly to the overall response rate at Day 28.

Other secondary endpoints that will be derived in the statistical analyses include, but are not limited to, the following:

- All-cause, transplant-related, infection-related and GvHD-related mortality: defined as the time from HSCT to death due to any cause, transplantation, infection and GvHD, respectively
- Duration of any overall and GI response

The secondary endpoints of overall survival and failure-free survival rate at different timepoints will be analyzed using the Cox proportional hazard model. The hazard ratio (and the corresponding 95% confidence interval) will be reported. A Kaplan-Meier plot will also be presented. All-cause, transplant-related, infection-related and GvHD-related mortality will be analyzed using a similar method with competing-risk taken into consideration.

The other time-to-event types of secondary endpoints, including duration of any overall response and any GI response, will also be analyzed using the Cox proportional hazard model and summarized using Kaplan-Meier plots.

The change from baseline in acute GvHD grading will be analyzed with a shift table.

All other secondary efficacy endpoints will be summarized with descriptive statistics.

Safety Analyses (Parts 1 and 2)

Secondary safety outcome measures will be summarized with descriptive statistics and qualitative analysis (see Section 8.4.2.2). Adverse events will be listed for each subject and summarized by system organ class and preferred term by using the Medical Dictionary for Regulatory Activities. Safety laboratory data, vital signs measurements and biomarker data will be listed for each subject and summarized with descriptive statistics by treatment group (Part 2 only), visit and assessment time.

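### Protocol Sections 10.6 and 8.2 conflict on how long AEs are observed after study treatment stops; if 10.6 governs, the Part 2 incidence summaries mix harm with observation time

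*Protocol*

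**What the plan says.** **Collection period.** Protocol Section 12.1.2: "All other AEs from the first IP exposure until study completion will be described on the AE CRF".

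**When completion occurs for a subject who stops treatment.** Under Section 10.6, if treatment stops before Day 28 and at least 2 weeks have passed since the last dose, "the Day 28 visit will serve as the study completion/termination visit". Otherwise the termination visit comes 2 weeks after the last dose, and the same applies to a stop after Day 28. The section adds: "Subjects who discontinue study treatment will not attend any other subsequent visits other than Day 28 and the study completion/termination visit". The one exception is follow-up of AEs that are already resolving. Footnote a to Tables 1 and 2 and footnote b to Table 1 repeat these rules. Subjects who do not stop early remain to Day 365 (about 52 weeks, Section 8.3).

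**The contrary statement.** Section 8.2, at the end of its text on treatment failures, says that every subject is followed at Days 100, 180 and 365. Earlier in the same section, subjects withdrawn from treatment are followed to Day 28 at a minimum, with a pointer to Section 10.6.

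**What ends treatment.** Treatment failure, including second-line therapy before Day 28 (Sections 8.2 and 9.3).

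**Analysis.** The Part 2 safety objective is comparative (Section 7.3.2). The outcomes are incidences of AEs and SAEs, recurrence of malignancy through Days 180 and 365, and "Incidence and type of infection (eg, bacterial, fungal, viral, etc) at Days 28, 56, 180 and 365" (Section 8.4.2.2). Section 13.4.2 says: "Secondary safety outcome measures will be summarized with descriptive statistics and qualitative analysis". Section 13.4 summarizes categorical variables as counts and frequencies. SAP Sections 8.5 and 8.6 use competing-risk cumulative incidence for malignancy and infection, but that SAP covers Part 1 only, and its Section 1 says that none will be written for Part 2.

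**The concern.** If Section 10.6 is followed, a subject's AE window is set by whether and when study treatment stops. Treatment failure is a main reason for stopping, and the trial is sized on the expectation that fewer GLASSIA subjects will be non-responders. A proportion of subjects with an event, taken over windows of different length, then reflects both the hazard and the time watched. An excess on GLASSIA could be real harm or simply longer observation, and late events in control failures would go unrecorded. Infection and malignancy at Days 180 and 365 are the most exposed, because stoppers have no scheduled visit at those times under Section 10.6.

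**Working it through.** **1. Design rates.** The plan gives no safety figure to reproduce, so I first confirm that the response rates used below are those behind the sample size. Inputs from Section 13.1: "Control group overall response rate of 40% across strata", 65% on GLASSIA, "1-sided family wise Type I error rate of 0.025", power 80%.
- Log odds ratio form: (1.960 + 0.842)² × (1/0.24 + 1/0.2275) / (ln 2.786)² = 64.0 per group.
- A gamma(-2) nonbinding beta spend at 50% information gives a stage 1 spend of 0.0538, a futility p-value of 0.3430 and an inflation factor of 1.033.
- 64.0 × 1.033 = 66.1, so 67 per group, as stated.

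The implied Day 28 non-response is 60% on control and 35% on GLASSIA.

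**2. Assumptions not given in the documents.** A share s of each arm stops early and is observed to Day 28; the rest are observed to Day 365. Deaths are ignored. The hazard is constant and equal in both arms. The 60/35% case treats every Day 28 non-responder as a stopper and is an upper case; 40/25% and 30/20% are milder.
- Mean window = 28s + 365(1 − s)
- Observed incidence = s × R(28) + (1 − s) × R(365), where R(t) = 1 − exp(−ht)

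| Stopping, control/GLASSIA | Mean window (days) | Apparent RR, true 1-year risk 10% to 80% |
|---|---|---|
| 60% / 35% | 163 / 247 | 1.51 to 1.44 |
| 40% / 25% | 230 / 281 | 1.22 to 1.19 |
| 30% / 20% | 264 / 298 | 1.13 to 1.11 |

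Example at 60/35% with a true risk of 50% in both arms: 23.1% observed on control and 34.3% on GLASSIA, RR 1.48. If stoppers are observed to Day 42, the ranges are 1.47 to 1.37 in the first row and 1.12 to 1.10 in the last.

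**3. What shrinks or reverses it.**
- *Early-clustered events.* If 80% of a year's events fall by Day 28, 60/35% stopping gives 26.4% vs 27.9%, 44.0% vs 46.5% and 70.4% vs 74.4% for true risks of 30%, 50% and 80%: 1.5 to 4.0 percentage points.
- *A 30-day post-dose limit.* SAP Section 8.2 counts treatment-emergent AEs to 30 days after the last dose. Carried into Part 2, completers would count to Day 49 + 30 = Day 79. At 60/35% the mean windows are 0.60 × 28 + 0.40 × 79 = 48 days and 0.35 × 28 + 0.65 × 79 = 61 days, ratio 1.26. With half of the non-responders stopping (30/17.5%) the ratio is 1.10.
- *Higher hazard in stoppers.* With 60/35% stopping and a 50% risk in the others, the apparent excess disappears at about a 13-fold hazard (49.9% vs 50.0%) and reverses at 15-fold (53.0% vs 51.7%). This is not absence of bias: at 13-fold, complete follow-up would show 80.0% vs 67.5%.

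**4. Checks on two possible remedies.**
- *Events per subject-time.* Take 60/35% stopping, a true 1-year risk of 40% and half of the events by Day 28. Incidence is 0.60 × 0.20 + 0.40 × 0.40 = 28% on control and 0.35 × 0.20 + 0.65 × 0.40 = 33% on GLASSIA. The rate ratio is (0.33/247)/(0.28/163) ≈ 0.78, falsely protective although the true risks are equal.
- *A Day 28 window alone.* Planned dosing is 90 + 6 × 30 + 6 × 120 = 990 mg/kg. Assessments precede the Day 28 infusion, so the doses on Days 28, 35, 42 and 49 (4 × 120 = 480 mg/kg, 48%) would fall outside the window.

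**The case against.** The strongest answer is Section 8.2: if every subject, including treatment failures, is followed to Day 365, most of the imbalance disappears. That stands as a condition. It does not settle the matter, because the specific rule for treatment stoppers is in Section 10.6 and in the schedule footnotes that sites would follow, and Section 8.2 itself points to Section 10.6.

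Second, Section 13.4.2 never uses the word crude and specifies no between-arm test of AEs. This is fair: the estimator is inferred from incidence outcomes, descriptive summaries and the absence of any adjustment. Infection at Day 28 is already listed, so one common time point exists for that outcome.

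Third, deaths. Section 6.2 gives 5% to 30% one-year survival for steroid non-responders. With exponential death times and all responders surviving, non-responders would contribute about 116 to 212 days even under complete follow-up. That gives a window ratio of 1.14 to 1.29 with no truncation at all. The upper case of 1.5 therefore cannot be attributed wholly to the follow-up rule.

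Fourth, the missing method could be called detail left for a Part 2 SAP. In part it is, but Section 13.4.2 already gives cause-specific mortality a competing-risk treatment and gives harms none.

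**Conclusion.** The concern holds conditionally. The documents contradict themselves on how long AEs are observed after study treatment stops. If the Section 10.6 rule governs, Part 2 harms would be summarized as incidences over windows linked to treatment failure, with nothing in Section 13.4.2 to allow for it. Under equal hazards, the arm with fewer failures tends to look more toxic: RR about 1.1 to 1.2 for moderate differences in stopping, and up to about 1.5 in the upper case. These figures rest on assumed stopping shares, a constant hazard and no deaths.

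A reader might infer that follow-up definitely ends at Day 28 for treatment failures, or that GLASSIA will look about 50% more toxic. The documents support neither. Section 8.2 says otherwise on follow-up, no stopping rates are given, and the direction depends on event timing and on the hazard in stoppers.

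The study was terminated with one subject enrolled and before Part 2 began, so this is a weakness of the plan that affects no reported result.

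**What to change.** 1. Reconcile Section 8.2 with Section 10.6 and the footnotes to Tables 1 and 2 on how long AEs are collected after study treatment stops.
2. In Section 13.4.2, estimate infection and malignancy at Days 180 and 365, and time to first AE or SAE of interest, by arm. Use cumulative incidence with death as a competing event and censoring at the last AE assessment. SAP Sections 8.5 and 8.6 already take this approach for infection and malignancy in Part 1.
3. Add a by-arm AE and SAE table from first dose through the Day 28 visit, the scheduled window that stoppers and non-stoppers share. Place it beside the full-period tables and not as the sole main comparison, since dosing continues to Day 49.
4. Do not rely on one events-per-subject-time rate over the full period. If rates are reported, split them by period, for example to Day 28, Day 28 to 56, and after Day 56.

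The cost of items 2 to 4 is protocol wording and a few tables. Item 1 is wording as well, unless it is resolved in favor of longer follow-up, which would add visits for stoppers. If follow-up does end at treatment stop, the later estimates still assume that this censoring is non-informative.

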13.4.3 Exploratory Outcome Measures

The exploratory outcome measures include GvHD VGPR, steroid use, GI CR and PR for each baseline GvHD severity grade, population PK, pharmacodynamics and health outcomes (see Section 8.4.3). Exploratory outcome measures will be summarized with descriptive statistics.

13.5 Planned Interim Analysis of the Study

Part 1

An analysis will be performed to determine whether continuation from Part 1 to Part 2 is warranted. It will be performed when the last subject in Part 1 has completed the GvHD response assessment at Day 28. The overall response rate at Day 28 will be analyzed, as well as the data collected at baseline, efficacy as measured by secondary efficacy outcome measures, and safety data.

The analysis will be assessed by the Sponsor. The study may proceed to Part 2 if an overall response rate of $\geq 55\%$ is observed at Day 28 in Part 1. The criteria for initiation of Part 2 are specified in Section 8.2.2.

Part 2

A group sequential design with 1 interim look (Part 2) will be applied to the study. The gamma error spending function³¹ with a parameter -2 will be used for beta spending (nonbinding). SAS version 9.4, PROC SEQDESIGN with stop=both and nonbinding option for beta, and a gamma parameter of -40 for alpha spending (and hence no alpha spent) and -2 for beta spending was used to calculate this design.

The interim analysis will take place when approximately 50% of the primary endpoint data for Part 2 has been accumulated (ie, approximately 67 evaluable subjects with Day 28 assessments).

An independent, unblinded biostatistics team will perform the interim analysis and present the results to the DMC. The study will be analyzed for futility based on the overall response at Day 28 in Part 2. The DMC will provide recommendations to the sponsor based on the interim analysis. However, the sponsor may decide to stop the trial even if statistical criteria for futility are not observed.

With the aforementioned spending functions, the DMC will recommend the study be stopped for futility if the nominal p-value is larger than 0.3430. The type II error spend at the interim analysis is 0.0538. As the interim analysis may not occur when exactly 50% of the primary endpoint data are accrued, the boundary may be adjusted at the analysis time using the specified gamma function (ie, a parameter of -2). A total of 134 evaluable subjects (67 per group) is planned.

14. DIRECT ACCESS TO SOURCE DATA/DOCUMENTS

The investigator/study site will cooperate and provide direct access to study documents and data, including source documentation for monitoring by the study monitor, audits by the sponsor or sponsor's representatives, review by the EC and inspections by applicable regulatory authorities, as described in the Clinical Trial Agreement (CTA). If contacted by an applicable regulatory authority, the investigator will notify the sponsor of contact, cooperate with the authority, provide the sponsor with copies of all documents received from the authority and allow the sponsor to comment on any responses, as described in the CTA.

15. QUALITY CONTROL AND QUALITY ASSURANCE

15.1 Investigator's Responsibility

The investigator will comply with the protocol (which has been approved/given favorable opinion by the EC), ICH GCP and applicable national and local regulatory requirements as described in the CTA. The investigator is ultimately responsible for the conduct of all aspects of the study at the study site and verifies by signature the integrity of all data transmitted to the sponsor. The term "investigator" as used in this protocol as well as in other study documents, refers to the investigator or authorized study personnel that the investigator has designated to perform certain duties. Sub-investigators or other authorized study personnel are eligible to sign for the investigator, except where the investigator's signature is specifically required.

